5.6.4. Multiple Comparison Adjustment for the Primary Efficacy Endpoint

The MMRM model above will test for the significance of treatment effect. Testing will continue

with each of the 4 doses of RPL554 against placebo, starting with the highest dose (6 mg).

To this end, the fixed-sequence testing approach (Maurer et al., 1995; (Westfall & Krishen, 2001)) will be used.

Let $i = 0, 1, \dots, 4$ represent increasing dose levels, 0 denoting placebo. Also, let μ_i , $i = 0, 1, \dots, 4$, denote the mean change from baseline in peak FEV₁ after 4 weeks of treatment for placebo and each increasing active dose level, respectively. The primary null hypotheses are defined as: $H_i: \mu_j - \mu_0 = 0$ and will be tested against the two-sided alternative $K_i: \mu_j - \mu_0 \neq 0$, $j = 1, \dots, 4$.

Finally, let p_1, \dots, p_4 denote the marginal p-values obtained from the statistical tests associated with H_1, \dots, H_4 (obtained from the MMRM model).

The fixed-sequence testing will begin with the null hypothesis corresponding to the highest dose versus placebo. If a statistically significant difference is found at the two-sided α level of 5%, the testing will proceed with the next highest dose, and so on. Otherwise, testing stops and the remaining null hypotheses are accepted without testing.

This testing strategy can be written as the following stepwise algorithm:

- Step 1: If $p_4 \leq \alpha$ reject H_4 and go to Step 2. Otherwise accept H_1, \dots, H_4 and stop.
- Step 2: If $p_3 \leq \alpha$ reject H_3 and go to Step 3. Otherwise accept H_1, \dots, H_3 and stop.
- Step 3: If $p_2 \leq \alpha$ reject H_2 and go to Step 4. Otherwise accept H_1 and H_2 and stop.
- Step 4: If $p_1 \leq \alpha$ reject H_1 . Otherwise accept H_1 .

The fixed-sequence procedure controls the family-wise error rate in the strong sense because, for each null hypothesis, the testing is conditional upon rejecting all hypotheses earlier in the sequence (Dmitrienko, et al., 2009).

5.6.5. Multiple Comparison Adjustment for the Secondary Efficacy Endpoints

As type I error is only controlled for the primary, secondary endpoints will be considered exploratory. Each secondary endpoint will be tested independently and nominally following a hierarchical testing of doses like the one used for the primary. Interpretation of the analyses of secondary endpoints in the CSR should ensure to consider the dose ranging nature of the study.

5.6.6. Examination of Subgroups

The following subgroups will be examined:

1. Current vs. ex-smokers
2. Chronic bronchitis vs. no chronic bronchitis at screening
3. Males vs. females.
4. Symptoms severity (MRC <2 vs. MRC \geq 2) at randomization
5. Age: (\geq 65 vs < 65)
6. Inhaled corticosteroid use versus no use (use of medications during the last 7 days of run-in phase).
7. By baseline FEV1 (> or \leq 50% predicted)

Subgroup analyses will be performed for the primary and the selected secondary endpoints (see 5.4).

The MMRM model will be run on each subgroup separately.

6. Safety Endpoints

Safety measures that will be collected and investigated include adverse events (AEs), clinical

laboratory tests, vital signs, physical examination and electrocardiograms assessments (ECGs, 12-Lead and using 24 hour Holter monitors).

All safety analyses will be performed on the safety analysis set. Patients will be analyzed according to the treatment received. All safety summaries will present the five treatment groups.

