4.3.4 Replacement Policy

It is planned to randomize approximately 400 patients. Discontinued patients in this study will not be replaced.

Verona Pharma plc CONFIDENTIAL Page 30 of 67

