5.7 Method of Assigning Patients to Treatment Groups

All patients consented will be assigned a patient identification (PID) number upon signing of the informed consent using the following convention: XXX-YYY where XXX is the center number and YYY is the patient number (001, 002, etc.). Patients will receive one of the five different treatment options in the study (see Section 5.1). Patients will be equally randomized to one of the four doses or placebo before the first study medication administration at Visit 2. Medication identification numbers will be provided on the study medication kit.

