3.3. Determination of Sample Size

The standard deviation for peak FEV1 is estimated to be 250 mL. With a 2-sided test at a 5% significance level and 80 evaluable patients per group, there will be an 80% power to detect a true difference of 111 mL between any two treatments. This detectable limit has been considered sufficient to conclusively identify a minimal effective dose of RPL554. Thus 80 patients per group will be randomized for a total of 400 patients.

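### Subgroup MMRMs are fitted level by level with no planned treatment-by-subgroup contrast, so the planned output contains no estimate of whether effects differ between levels

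*SAP*

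**What the plan says.** SAP 5.6.6 lists seven factors, each with two levels: smoking status, chronic bronchitis, sex, MRC grade, age, inhaled corticosteroid use and baseline FEV1 % predicted. It states: "Subgroup analyses will be performed for the primary and the selected secondary endpoints", with a pointer to SAP 5.4. The method is then given in full: "The MMRM model will be run on each subgroup separately".

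The model meant is the one in SAP 5.6.2 and Appendix 4: treatment, visit, treatment-by-visit and baseline. The Appendix 4 code requests LS-mean differences with confidence limits. Neither these places nor SAP 5.6.3 contains a subgroup term, a treatment-by-subgroup term or a rule for reading results that differ between levels.

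Two other places bear on interpretation. SAP 5.4 describes subgroup analyses as a kind of sensitivity analysis. SAP 5.6.5 says type I error is controlled for the primary endpoint only and treats secondary endpoints as exploratory. For country, which is not one of the seven factors, Protocol 9.2.2.5 allows either separate models or a treatment-by-country interaction model, with no formal test.

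**The concern.** A subgroup analysis asks whether the treatment effect differs between levels. Separate fits answer another question: whether each level, taken alone, shows a difference from placebo. Each level has fewer patients than the whole trial, so its result can miss significance for lack of numbers alone. If one level reaches p < 0.05 and the other does not, that is not evidence that the effects differ. With no planned contrast and no reading rule, that comparison is the one the output most readily offers.

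At stake is how subgroup results are read when later work is planned from this dose-ranging trial. The primary conclusion is not at stake.

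**Working it through.** **Inputs.** SAP 3.3 assumes an SD of 250 mL for peak FEV1, a two-sided 5% level and 80 evaluable patients in each arm. From these it concludes that "there will be an 80% power to detect a true difference of 111 mL between any two treatments". Allocation is equal across the five arms (Protocol 5.7), 400 patients in all. The documents give no subgroup sizes, so the splits below are assumptions, taken to be the same in every arm. No gain from baseline adjustment or repeated measures is counted. No dropout is allowed for, although Protocol 4.3.4 says "Discontinued patients in this study will not be replaced".

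**Plan's own figure.** SE of a dose-placebo difference = 250 × sqrt(2/80) = 39.5 mL. Power at 111 mL = Φ(111/39.5 − 1.96) = 80.2%. The difference detectable with 80% power is 2.80 × 39.5 = 110.7 mL. The stated design reproduces.

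**Within one level, even split (40 per arm).** SE = 250 × sqrt(2/40) = 55.9 mL. Let p be the two-sided power in one level. The levels contain different patients, so the chance that exactly one is significant is 2p(1 − p).

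| Uniform true effect | Effect / SE | p per level | Exactly one significant |
|---|---|---|---|
| 60 mL | 1.07 | 0.189 | 31% |
| 111 mL | 1.99 | 0.510 | 50% |
| 150 mL | 2.68 | 0.765 | 36% |
| 200 mL | 3.58 | 0.947 | 10% |

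The function 2p(1 − p) peaks at p = 0.5, so 111 mL with an even split lies almost exactly at the maximum.

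**Uneven splits at 111 mL.** The chance is p1(1 − p2) + p2(1 − p1).
- 30:70 (24 and 56 per arm): powers 0.337 and 0.652, giving 55%.
- 20:80 (16 and 64 per arm): powers 0.241 and 0.709, giving 61%.

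**Number of contrasts.** The list in SAP 5.4 repeats the primary endpoint, so there are three distinct endpoints. At Week 4, 7 factors × 2 levels × 4 doses × 3 endpoints = 168. If no dose affected any endpoint, 168 × 0.05 = 8.4 would be expected to reach nominal significance, about 4.2 in each direction.

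**What an interaction contrast would deliver.** SE = sqrt(SE1² + SE2²).
- Even split: sqrt(55.9² + 55.9²) = 79 mL. The 95% CI half-width is 1.96 × 79 = 155 mL. Power for a 111 mL difference in effect is 29%, and 221 mL is detectable with 80% power.
- 20:80 split: sqrt(88.4² + 44.2²) = 99 mL. The half-width is 1.96 × 98.8 = 194 mL. Power is 20%, and 277 mL is detectable with 80% power.

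When the true effect is uniform, this contrast wrongly signals a difference 5% of the time per factor and dose.

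**The case against.** **The difference can be recovered by hand.** A reader might infer that the plan makes it impossible to say whether effects differ. It does not. Appendix 4 asks for differences with confidence limits, and the two levels hold different patients, so the between-level difference and its SE can be computed from the planned output. What is missing is the prespecified contrast.

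**The results already carry a modest label.** A reader might infer that the SAP sets up subgroup claims. SAP 5.6.6 attaches no hypothesis or significance rule, and SAP 5.4 calls these sensitivity analyses in a list that includes Week 4 peak FEV1. That stands, but neither place says how discordant levels should be read.

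**The 50% is a chosen point.** The 111 mL figure is the detectable limit, not a stated expected effect, and it lies near the maximum for an even split. This stands, which is why the range is shown.

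**The 8.4 needs qualifying.** The contrasts are correlated: doses share one placebo arm, the endpoints come from the same spirometry, and the factors re-divide the same patients. Correlation leaves the expected count unchanged but makes the actual count more variable. The count also supposes that no dose affects any endpoint.

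**Covariance.** A reader might infer that separate fits are unreliable because each estimates a 5×5 unstructured matrix from a fraction of the patients. That size applies only to peak FEV1. Under SAP 5.2, trough has four visits (4×4) and the 12-hour average two (2×2). The matrix is shared across treatment groups, so an even split estimates at most 5 × 6 / 2 = 15 parameters from about 200 patients, and SAP 5.6.2 provides a fallback for non-convergence. The documents show no harm here.

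**An interaction estimate would be imprecise.** True, and it would seldom settle heterogeneity. That is a reason to report an interval and not lean on a p-value; it does not justify leaving the estimate out.

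**Conclusion.** The gap is real and limited. The planned output shows nominal dose-placebo results per level and no estimate of whether effects differ between levels. With a uniform effect and an even split, one level alone would be significant in roughly 10% to 50% of cases for true effects of 60 to 200 mL, and in up to 61% at 111 mL with a 20:80 split. These figures are illustrations. They rest on assumed splits, SD 250 mL in every level, a normal approximation and no dropout.

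It is a minor to moderate reporting improvement. The primary fixed-sequence test, the sample size and the conduct of the trial are unaffected.

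**What to change.** For each factor, fit one MMRM on the full analysis set. To the SAP 5.6.2 terms, add subgroup, treatment-by-subgroup, visit-by-subgroup and treatment-by-visit-by-subgroup. If the flexibility of separate fits is wanted, also add a baseline-by-subgroup term and let the covariance differ by level (the `group=` option on the REPEATED statement). Alternatively, keep the separate fits and compute the between-level difference from the two independent estimates, with SE = sqrt(SE1² + SE2²).

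Report, each with a 95% CI, the Week 4 dose-placebo difference in each level and the interaction contrast for each dose. Add three statements to SAP 5.6.6:
- the subgroup results are descriptive;
- per-level p-values are not evidence that effects differ;
- a non-significant interaction is not evidence of consistency, because power is only about 20-29% for a 111 mL difference in effect.

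The cost is a short SAP addendum, a modified PROC MIXED call and a little more analysis work. No new data are needed. If level-specific covariance is not used, the single model imposes one covariance across levels.

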6.1. Adverse Events

Treatment Emergent Adverse Events (TEAEs) are defined as all AEs which start after the first dose of study medication, or start prior to first dose of study medication and worsen, based on the investigator assessment of severity, on or after first dose of study medication.

Adverse events with completely missing onset dates will also be considered as treatment emergent. If any AE records contain only partial dates, these will be handled by imputation, as described in Section 3.8.4.

Table summaries will be produced summarizing AEs in the following ways:

- TEAEs
- TEAEs classified by maximum severity
- TEAEs classified with relationship to study medication
- TEAEs leading to study discontinuation
- Serious TEAEs
- Serious TEAEs classified by maximum severity
- Serious TEAEs classified with relationship to study medication
- Serious TEAEs leading to study discontinuation
- TEAEs with outcome death

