4.3.1 Study Medication Discontinuation

Study medication must be discontinued for the following reasons:

- Unacceptable toxicity related to study medication
- Intolerable or persistent adverse events of any severity
- General or specific changes in the patient's condition rendering the patient unacceptable for further treatment in the judgment of the Investigator
- Development of a COPD exacerbation, which necessitates use of oral or parenteral corticosteroids and/or antibiotics.
- Reduction from baseline (Visit 2) in pre-dose FEV₁ >20% that requires use of albuterol/salbutamol >12 puffs per day for at least 3 consecutive days associated with an increase in COPD symptoms.
- Pregnancy

Verona Pharma plc CONFIDENTIAL Page 28 of 67

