7.6.2.4 Action and Outcome

- Action taken with study medication (none, study medication stopped, study medication temporarily interrupted)
- Other actions (none, concomitant medication, study discontinuation, hospitalization, other)
- The outcome and date of outcome according to the following definitions:
 - Recovered or resolved (adverse event disappeared)
 - Recovering or resolving (patient is recovering)
 - Not recovered or not resolved (adverse event remains without signs of improvement)
 - Recovered or resolved with sequelae (adverse event has resulted in permanent disability or incapacity)
 - Fatal
 - Unknown (only applicable if patient has been lost to follow-up)
- Seriousness (yes or no)

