Average EXACT-PRO total scores, average daily use of rescue medication, SGRQ-C total scores, MRC, global assessment of change, and TDI scores will be compared between the five treatments using ANCOVA models with treatment and country(/center) as factors and using baseline as a covariate where appropriate. Subdomain scores of the EXACT-PRO and SGRQC will be summarized and subjected to exploratory analyses.

The number of COPD exacerbations will be summarized by treatment group.

Testing for efficacy will start with the highest dose of RPL554 versus placebo. If a statistically significant difference is found, the testing will proceed with the next highest dose, and so on. Secondarily, the various doses of RPL554 will be compared. Appropriate measures will be taken to control for the type I error rate in these hypothesis tests. A closed testing procedure to test active dose vs. placebo will be used for the primary endpoint. The study is not powered for pairwise differences between active doses. Thus, dose-response is best investigated in a secondary analysis fitting an appropriate dose-response model to the data. The Statistical Analysis Plan will provide additional details of the multiplicity adjustment method(s) used.

All hypothesis testing will be done using two-sided alternative hypotheses. P-values less than 5% will be considered statistically significant.

9.2.2.6 *Safety*

Safety data, including safety laboratory tests, ECG parameters, Holter monitors, vital signs and physical examinations, will be summarized by treatment group and time point, when appropriate. For continuous variables, the change from baseline (both regarding pre-dose at Visit 2 and pre-dose at each treatment visit) to each post-dose time point will also be calculated and summarized. Data will further be illustrated by shift tables (showing changes from low/normal/high) and shift plots for selected time points.

Coded adverse event terms will be presented by system organ class (SOC) and preferred term and summarized by treatment group. A summary table by treatment group with total number and number of patients with adverse events, SAEs, adverse events leading to discontinuation of study medication, causally related adverse events and severe adverse events will be produced. Further SAEs, causally related adverse events and adverse event of each intensity will be summarized by SOC and preferred term.

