6.1.1. Analysis of Adverse Events

Adverse events will be coded using MedDRA version 20 (June 2017).

All AE tables will be summarized by SOC and PT by treatment group, including the number of patients for each SOC and PT. Within each patient, multiple records of events mapping to a common MedDRA PT and SOC will be condensed into a single AE for incidence counts. Adverse Events will be reported by SOC and by PT in decreasing order of the highest active dose group of study medication (i.e 6.0 mg).

Listings of patients who discontinue the study for an AE, patients who experience an SAE and patients with AEs resulting in death will be presented.

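### The SAP replaces the protocol's count of adverse events leading to discontinuation of study medication with adverse events leading to study discontinuation, and does not declare the change

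*SAP*

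**What the plan says.** Protocol 9.2.2.6 (Safety) plans a summary table by treatment group, with event totals and patient counts. Its categories include "adverse events leading to discontinuation of study medication, causally related adverse events and severe adverse events will be produced".

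SAP 6.1 lists the adverse event tables to be produced. The two on discontinuation are "TEAEs leading to study discontinuation" and "Serious TEAEs leading to study discontinuation". SAP 6.1.1 adds this: "Listings of patients who discontinue the study for an AE, patients who experience an SAE and patients with AEs resulting in death will be presented". None of the three is defined by stopping the drug.

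Protocol 7.6.2.4 sets out what is recorded for each adverse event. One item is "Action taken with study medication (none, study medication stopped, study medication temporarily interrupted". A separate item is "Other actions (none, concomitant medication, study discontinuation, hospitalization, other".

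Protocol 4.3.1 gives the reasons for which study medication must be discontinued, among them "Intolerable or persistent adverse events of any severity". Patient withdrawal has its own section, 4.3.2.

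SAP 3.4 names two changes to the planned analyses: MMRM in place of LOCF ANCOVA, and a new per-protocol set.

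**The concern.** The trial compares four doses with placebo. Safety is a secondary objective (Protocol 2.2), and Protocol 3.2 says the four-dose design is meant to allow dose-dependent effects on safety to be examined. The number of patients at each dose whose drug was stopped because of an adverse event is one of the safety counts the protocol promised. The SAP provides a different count under a similar name. If the two differ in practice, the promised count is not in the planned output, and a reader of the study report could take the study-discontinuation table for it.

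**Working it through.** The documents give no rate of adverse-event-related drug stops, so there is no planned figure to reproduce. The check is a comparison of text, followed by an illustration on assumed values.

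**Step 1. Are the two terms interchangeable in these documents?** No.

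| Place | Drug stopped | Study left |
|---|---|---|
| Protocol 7.6.2.4, adverse event record | an option under action taken with the drug | an option under other actions |
| Protocol 4.3.1 and 4.3.2 | own section | own section |
| Protocol 9.2.2.6, planned summary | yes | not mentioned |
| SAP 6.1, tables | no | yes, for all and for serious TEAEs |
| SAP 6.1.1, listing | no | yes |
| SAP 4.1, disposition | no | yes |

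**Step 2. Does stopping drug for an adverse event imply leaving the study?** For a COPD exacerbation, 4.3.1 stops drug and 4.3.2 ends participation. For pregnancy, 4.3.1 stops drug, and 4.3.2 and 7.6.4 require withdrawal. For unacceptable toxicity and for intolerable or persistent adverse events, 4.3.1 stops drug and no section says that the patient then leaves. The text therefore leaves room for a patient with drug stopped and no study discontinuation recorded.

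**Step 3. Does another SAP output supply the missing count?** SAP 4.1 counts discontinuation from the study only. SAP 4.5.2 gives duration of exposure without a reason for stopping. The event would appear in the overall, severity and relationship tables of SAP 6.1, and SAP 3.7 lists all available data. None of these gives, by dose, the number of patients whose drug was stopped for an adverse event.

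**Step 4. Is the change declared?** SAP 3.4 does not mention it.

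**Step 5. How large could the gap be?** Let *k* be the patients in an arm of 80 (the planned group size, SAP 3.3) whose drug is stopped for an adverse event. Let *s* be the share of them not recorded as discontinuing the study. Both are assumptions. Taking every other patient in *k* to be recorded as leaving for the event:

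- Protocol count = 100 × *k* / 80
- SAP count = 100 × *k* × (1 − *s*) / 80

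| *k* | Protocol | SAP, *s* = 0 | SAP, *s* = 0.25 | SAP, *s* = 0.5 | SAP, *s* = 1 |
|---|---|---|---|---|---|
| 4 | 4/80 = 5.0% | 4/80 = 5.0% | 3/80 = 3.75% | 2/80 = 2.5% | 0% |
| 8 | 8/80 = 10.0% | 8/80 = 10.0% | 6/80 = 7.5% | 4/80 = 5.0% | 0% |

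The gap runs from nothing to the whole count. The documents do not say where in that range the trial would fall.

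**The case against.** The strongest reply is that under this design the two counts may coincide. Visits 3 to 6 are all dosing visits with spirometry timed to the dose, and no schedule exists for patients off drug. Exacerbation and pregnancy, the two drug-stop reasons for which the protocol also addresses study participation, both end it. SAP 3.7.5 confines the assessments analyzed to the period from first to last dose plus one day, so off-drug follow-up was not planned for. In addition, the events are not lost from the tables and listings, and Protocol 9.1 requires any deviation from the specified analysis to be explained in the study report.

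Most of this stands and limits the size of the point. It does not remove the point: 4.3.1 does not require study exit for the other adverse events, the record keeps the two outcomes apart, and the protocol named one while the SAP tabulates the other. Later explanation in the report does not supply the count.

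A reader might infer more than the documents support:

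- **A patient who stops drug and still attends the final visit goes uncounted.** Not so. Protocol 4.3.2 calls withdrawn patients for a final visit, and the schedule labels Visit 6b as also serving early termination. Such a patient has discontinued the study and is counted. Only a patient not recorded as discontinuing is missed.
- **The SAP count can only be equal or lower.** That is the normal case, but an event could be marked as study discontinuation with no drug action recorded.
- **The SAP makes a poorly tolerated dose look better, on the main tolerability comparison.** The documents give no share who stay, no difference in that share between arms, and no ranking of this category above the others in 9.2.2.6.
- **Temporary interruptions must be summarized.** They are collected, but 9.2.2.6 does not ask for a summary of them.

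**Conclusion.** The mismatch between protocol and SAP is certain on the text: a safety summary named in Protocol 9.2.2.6 has been replaced in SAP 6.1 and 6.1.1 by one built on a different data item, without declaration in SAP 3.4. The consequence is limited to the discontinuation count and its dedicated listing. Its size is unknown and may be zero; it depends wholly on how many patients stop drug for an adverse event without being recorded as leaving the study. A systematic understatement of poor tolerability at any dose is not shown. The correction is still worth making, because it restores a planned by-dose count at almost no cost.

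**What to change.** In SAP 6.1, add a table by treatment group of TEAEs for which the recorded action was that study medication was stopped (Protocol 7.6.2.4), and the same for serious TEAEs. The first restores what Protocol 9.2.2.6 specifies; the second mirrors the SAP's own split by seriousness. In SAP 6.1.1, add the matching patient listing. Keep the study-discontinuation tables and listing as a separate, clearly labeled category, and state which recorded item feeds each. If the sponsor prefers to report study discontinuation only, SAP 3.4 should declare and justify the departure from the protocol.

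The cost is some SAP wording, one or two extra tables and a listing, all from a field already collected. No efficacy analysis changes. A line for temporary interruptions is optional.
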